#### **10.5.2.4 Other safety data**

Data from other tests (e.g. vital signs) will be listed, notable values will be flagged, and any other information collected will be listed as appropriate.

#### **10.5.2.5 Supportive analyses for secondary objectives**

Not applicable

#### **10.5.2.6 Tolerability**

Tolerability of study treatment will be assessed by summarizing the number of dose interruptions and dose reductions. Reasons for dose interruption and dose reductions, cumulative dose and dose intensity will be listed by patient.

### **10.5.3 Pharmacokinetics**

Concentrations will be expressed in mass per volume units.

Valid  $C_{min}$  is defined as a pre-dose sample collected at steady-state, at 24 +/- 4 hours after the last dose, and collected prior to the next dose.

Steady-state condition for  $C_{min}$  is defined as no dose interruption/adjustment in the last 4 days prior to the pre-dose sample, no vomiting within 4 hours following study drug administration on the day of or the day before pharmacokinetic blood sampling.

Valid  $C_{2h}$  is defined as a 2 hour post-dose sample collected at steady-state.

Steady-state condition for  $C_{2h}$  is defined as no dose interruption/adjustment in the last 4 days prior to the  $C_{2h}$  sample, no vomiting within 4 hours following study drug administration on the day of or the day before pharmacokinetic blood sampling.

$C_{min}$  and  $C_{2h}$  of everolimus will be both summarized by treatment group, and by actual lead dose, for patients with valid PK samples.

To assess the effect of everolimus on exemestane exposure,  $C_{min}$  and  $C_{2h}$  of exemestane with and without co-administration of everolimus will be compared separately after log-transformation using an ANOVA model with treatment as a fixed effect.  $C_{min}$  and  $C_{2h}$  ratios with everolimus to those without everolimus and their 90% CI will be calculated from the fitted models.

To assess the effect of everolimus on estradiol ( $E_2$ ) level, changes in estradiol levels from baseline to week 4 will be summarized for the patients with valid PK samples. The relationship between everolimus  $C_{min}$  and change from baseline in estradiol at Week 4 will

also be analyzed by a model-based approach. This analysis will be repeated adjusted by the concomitant use of moderate/strong CYP3A4/PgP inducer/inhibitor via an appropriate covariate in the model.

$C_{min}$  and  $C_{2h}$  will be analyzed based on with or without concomitant use of CYP3A4/PgP moderate/strong inhibitor or inducer to assess their effect on exposure of everolimus

Population PK models will be used to identify and quantify potential covariates that influence everolimus PK. Details of this analysis will be covered in a separate document.

A model-based approach will be used to explore:

- the potential relationships between efficacy (measured by appropriate efficacy endpoints such as PFS) and everolimus exposure based on  $C_{min}$
- the potential relationship between appropriate safety endpoints and everolimus exposure based on  $C_{min}$  or  $C_{2h}$
- the potential relationship between efficacy (measured by appropriate efficacy endpoints such as PFS) and changes in Estradiol ( $E_2$ ) assuming a DDI of everolimus with exemestane

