Secondary Objectives	
 
• To assess PFS in the two treatment arms as determined by a Blinded Independent Review Committee (BIRC).
 
• To assess overall survival (OS) in the two treatment arms
 
• To assess the following efficacy endpoints in the two treatment arms based on both local investigator's assessment and BIRC 
 
• Overall response rate (ORR)
 
• Clinical benefit rate (CBR)
 
• Time to response and duration of response
 
 
 
• To assess time to deterioration of ECOG Performance Status
 
• To characterize the safety and tolerability of everolimus and exemestane versus placebo and exemestane
 
• Characterize the pharmacokinetics of everolimus (<math>C_{min}</math>, <math>C_{2h}</math>) when administered in combination with exemestane
 
• Compare the two treatment arms with respect to pre-dose concentration (<math>C_{min}</math>) and concentration at 2 hours post dose (<math>C_{2h}</math>) of exemestane and to compare the two treatment arms with respect to estradiol (E2) changes from baseline.
 

Study design	
Refer to Section 4.
 
This is a multicenter, double-blind, randomized, placebo-controlled, phase II study evaluating treatment with everolimus (10 mg daily) versus placebo in combination with exemestane (25 mg daily) in Chinese postmenopausal women with locally advanced, recurrent or metastatic, ER positive, HER-2 negative breast cancer refractory to non-steroidal aromatase inhibitors.
 
Approximately 160 patients will be randomized in 1:1 ratio to receive either everolimus or matching placebo in a blinded manner in addition to open label exemestane.
 
Screening phase:
 
Written informed consent must be obtained before any study specific medical procedures are performed. The investigator or his/her authorized designee will assign a unique number to patients being considered for the study.
 
After the patient signs the informed consent and prior to the first dose of study

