### **7.2.3 Pharmacokinetics**

Pharmacokinetic blood sample collection and handling are described in [Section 7.2.3.1](#).

Blood samples for Estradiol (E2) levels will be obtained at screening (or at Day 1 prior to study treatment) and at Cycle 1 Weeks 4 or any later one of the scheduled visits. This will allow evaluation of changes in estradiol levels after 4 weeks of study treatment.

Pre-dose blood samples for everolimus and exemestane trough levels will be collected at steady state at Cycle 1 Week 4 or any one of later scheduled visits. Steady-state is defined as having no dose adjustment/interruption of everolimus and exemestane in the previous 4 days prior to the day of the pre-dose PK sample collection.

On the days of pre-dose PK sample collection, patients should come back to the clinic to get their medications and ingest the medications at the clinic immediately after collection of the pre-dose blood samples. These pre-dose blood samples will allow determination of Cmin for everolimus and exemestane.

Patients who have ingested their medications at home prior to the study visit or have dose adjustment/interruption in the previous 4 days should not have their PK blood samples collected at that study visit, and the collection of the PK blood samples will be postponed to the next scheduled visit.

The collection date and time of all pre-dose PK samples must be documented (both for everolimus and exemestane, separately) in the Pharmacokinetic Blood Collection eCRF pages. The exact date and time of the everolimus and exemestane doses administered on the previous day prior to the visit day for the pre-dose PK sample must be entered on the eCRF. In addition, the exact date and time of the everolimus and exemestane doses administered immediately after the pre-dose PK sample collection on the visit day must be entered on the eCRF.

If the patient vomits within the first 4 hours following study-drug administration on the day of or the day before pharmacokinetic blood sampling, the time (using the 24-hours clock) of vomiting should be recorded on the AE eCRFs, and the collection of the PK blood samples will be postponed to the next scheduled visit.

No additional trial medication should be taken that day in an effort to replace the study drug that has been vomited.

If everolimus administration has been interrupted due to study drug suspected toxicities, then the PK sample collection should be postponed to the next visit.

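### The estradiol objective is to compare the arms, but Protocol 10.5.3 specifies no between-arm estimate or confidence interval, and its analysis set depends on events after randomisation

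*Protocol*

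**What the plan says.** The Protocol summary sets a secondary objective "to compare the two treatment arms with respect to estradiol (E2) changes from baseline". Table 3-1 of the Protocol and SAP section 1.2 repeat it. In all three places it shares a single objective with the arm comparison of exemestane Cmin and C2h.

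Protocol 10.5.3 treats the two halves differently. Exemestane Cmin and C2h with and without everolimus "will be compared separately after log-transformation using an ANOVA model with treatment as a fixed effect", and ratios with 90% CIs follow from the model. For E2, "changes in estradiol levels from baseline to week 4 will be summarized for the patients with valid PK samples". The relationship between everolimus Cmin and E2 change will "also be analyzed by a model-based approach".

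The same section makes validity depend on conditions around sampling. Steady state for Cmin "is defined as no dose interruption/adjustment in the last 4 days prior to the pre-dose sample", together with "no vomiting within 4 hours following study drug administration on the day of or the day before pharmacokinetic blood sampling". A valid Cmin must also be drawn 24 ± 4 hours after the previous dose.

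On collection, Protocol 7.2.3 says patients with "dose adjustment/interruption in the previous 4 days should not have their PK blood samples collected at that study visit". Sampling moves to the next scheduled visit. Follow-up E2 is drawn "at Cycle 1 Weeks 4 or any later one of the scheduled visits".

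The supplied SAP is for the final study report. Its section 1.2 says the PK analyses are not repeated and were covered in the primary report (data cut-off 19 May 2020). Its section 4 declares no change from the protocol.

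**The concern.** An objective worded as a comparison needs a contrast between arms and a measure of its uncertainty. This trial relies on estimation rather than testing (Protocol 10.6), so an estimate with its interval is the only form in which it can answer a comparative question. The E2 text supplies neither.

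The question has substance. Protocol 1.2.1.2.2 reports that in the earlier phase III trial exemestane Cmin and C2h were 45% and 64% higher when given with everolimus. The arm contrast in E2 is the direct check on whether that interaction alters estrogen suppression. Without a stated model, set and scale, the reader gets summary statistics and must form the comparison informally, or the analyst chooses the method after seeing the data.

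The second issue is the set. Dose interruption, dose adjustment and vomiting happen after randomisation and can be caused by treatment. If they remove different kinds or numbers of patients in the two arms, the retained groups are no longer fully comparable.

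**Working it through.** The plan states no sample size, power or precision figure for E2. Its only precision figure, the 90% CI of (0.45, 0.85) for a PFS hazard ratio of 0.62 with 110 events, reproduces: 0.62 × exp(±1.645 × √(4/110)) = 0.453 to 0.848. It has no bearing on E2. The main check is therefore a comparison of texts.

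**1. Does any planned E2 analysis give an arm contrast?**
- The summary of change: no contrast, no interval, no baseline covariate, and no statement that it is by arm.
- Everolimus Cmin against E2 change: this is exposure-response. Placebo patients have no everolimus exposure, so it cannot stand in for the randomised comparison.
- Efficacy against E2 change (end of 10.5.3): a different question.
- Supplied SAP: no E2 analysis.

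None does.

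**2. Is the set fixed at randomisation?** No. The dose-stability and vomiting conditions are post-baseline. The set is also narrower than the PK set of 10.1.3, which takes any patient with a concentration on record. The text does not say which analyte makes a placebo patient's sample valid.

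**3. Could exclusions differ by arm?** It is plausible. Table 1-3 shows, in Asian patients, stomatitis in 80% on everolimus against 16% on placebo, and pneumonitis in 23% against none. Table 6-3 calls for interruption for several toxicities. No rate of interruption, vomiting or invalid samples around week 4 is given.

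Illustration with assumed values: let a fraction e of the everolimus arm and p of the placebo arm be excluded, and let excluded patients differ from retained ones by d SD in both arms. The bias is (e − p) × d.
- Low: (0.20 − 0.10) × 0.25 = 0.025 SD.
- High: (0.40 − 0.10) × 0.50 = 0.15 SD.

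**4. What might baseline adjustment add?** Assume equal variances at both times (SD = 1 on the log scale) and correlation r, neither of which the documents give. The change-score variance is 2(1 − r), the ANCOVA variance is 1 − r², and their ratio is (1 + r)/2. The 90% CI half-width is 1.645 × √variance × √(2/n), with n = 80 per arm (160 randomised 1:1, all evaluable).

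| r | change variance | ANCOVA variance | ratio | half-width, change | half-width, ANCOVA |
|---|---|---|---|---|---|
| 0.3 | 1.40 | 0.91 | 0.65 | 0.308 SD | 0.248 SD |
| 0.5 | 1.00 | 0.75 | 0.75 | 0.260 SD | 0.225 SD |
| 0.7 | 0.60 | 0.51 | 0.85 | 0.201 SD | 0.186 SD |

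ANCOVA still answers the objective as worded. With log baseline in the model, the treatment coefficient is the same whether the response is log follow-up E2 or log change.

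**The case against.** **The plan does more than summarise E2.** True: it has two further models involving E2. Neither compares the arms, so the gap is confined to the between-arm question. The E2 sentence opens by naming the effect of everolimus as its aim, which suggests a display by arm. A display still lacks an estimate and an interval.

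**The primary report may contain the comparison.** A reader might infer that the trial never produced it. The documents do not support that. The SAP for the primary report is not supplied, nor is SAP Addendum 1, which the supplied SAP cites only for sample size.

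**The selection is asserted, not shown.** A reader might infer that the validity rule removes everolimus patients preferentially and breaks the randomised comparison. The documents give no exclusion rates, and a patient who fails the rule is resampled at a later visit. Only those who never reach an eligible visit are lost. Differential exclusion remains possible and unquantified. Postponement also brings its own gap: the analysis is called a change to week 4, yet a value may come later, with no stated handling.

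**The wider set is also selected.** This stands. Patients who stop before sampling have no follow-up E2. Table 7-5 lists E2 within the PK blood schedule, so the postponement rule in 7.2.3 appears to govern its collection too.

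**Change scores already use baseline.** Correct. It would be wrong to say the baseline is wasted; ANCOVA is a matter of efficiency. Reading the ratios above as 18% to 54% more patients (1/0.85 to 1/0.65) for this trial would also go too far, since r and the equal variances are assumed. Equal variances are uncertain for a hormone that exemestane lowers.

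**Conclusion.** The point holds as a mismatch between objective and analysis in the protocol text, which the supplied SAP leaves unchanged. The objective says compare, and no between-arm E2 estimate or CI is specified. This rests on the wording alone.

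The concern about the set is a possibility of unknown size. Under the assumed exclusions the bias is 0.025 to 0.15 SD, below the ANCOVA half-widths of 0.186 to 0.248 SD at 80 per arm, but the inputs are not from the trial. The precision gain from baseline adjustment is likewise illustrative.

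The importance is low. This is half of one secondary pharmacodynamic objective, and the PFS, OS, response and safety analyses do not depend on it.

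**What to change.** - Analyse log on-treatment E2 by ANCOVA with treatment and log baseline E2. Report the adjusted geometric mean ratio (everolimus arm to placebo arm) with its 90% CI, and the geometric means by arm.
- Include all patients with a baseline and an on-treatment E2 sample. State that this reduces selection but does not remove it, and report by arm how many patients lack a sample and why.
- State how values below the E2 assay limit of 2.0 pmol/L (Protocol 7.2.3.2) enter a log-scale analysis, and how samples postponed beyond week 4 are handled.
- Keep the valid-sample subset as a sensitivity analysis and for the exposure-response model, and say which analyte defines validity in the placebo arm.
- If the analysis is added now, label it as added after the primary cut-off. If the SAP for the primary report already holds an equivalent analysis, a cross-reference is enough.

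The cost is a few lines of analysis text and one table, with no new samples or visits.

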- For more severe toxicity (grade 2 in which case patients have pain but are able to maintain adequate oral alimentation, or grade 3 in which case patients cannot maintain adequate oral alimentation), the suggested treatments are topical analgesic mouth treatments (i.e., local anesthetics such as benzocaine, butyl aminobenzoate, tetracaine hydrochloride, menthol, or phenol) with or without topical corticosteroids, such as triamcinolone oral paste 0.1% (Kenalog in Orabase®).
- Agents containing alcohol, hydrogen peroxide, iodine, and thyme derivatives may tend to worsen mouth ulcers. It is preferable to avoid these agents.
- Antifungal agents must be avoided unless a fungal infection is diagnosed. In particular, systemic imidazole antifungal agents (ketoconazole, fluconazole, itraconazole, etc.) should be avoided in all patients due to their strong inhibition of everolimus metabolism, therefore leading to higher everolimus exposures. Therefore, topical antifungal agents are preferred if an infection is diagnosed. Similarly, antiviral agents such as acyclovir should be avoided unless a viral infection is diagnosed.

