#### **6.4.3 Other concomitant medications**

Everolimus is a substrate of CYP3A4, and a substrate and moderate inhibitor of the multidrug efflux pump, PgP (PgP, MDR1, and ABCB1). Therefore, extent of absorption and subsequent elimination of systemically absorbed everolimus may be influenced by products that are substrates, inhibitors, or inducers of CYP3A4 and/or PgP. Co-administration with strong inhibitors of CYP3A4 or PgP should be avoided. Co-administration with moderate CYP3A4 inhibitors (e.g., erythromycin, fluconazole) or PgP inhibitors should be used with caution. Seville orange, star fruit, grapefruit and their juices affect CYP3A4 and PgP activity. Concomitant use should be avoided.

Please refer to [Table 6-8](#) listing relevant inducers and inhibitors of CYP3A and to [Table 6-9](#) for a list of relevant substrates, inducers, and inhibitors of PgP.

Everolimus may affect the response to vaccinations making the response to the vaccination less effective. Live vaccines should be avoided while a patient is treated with everolimus.

**Table 6-8      Clinically relevant drug interactions: inducers, and inhibitors of isoenzyme CYP3A****Inducers****Strong inducers:**

avasimibe, carbamazepine, mitotane, phenobarbital, phenytoin, rifabutin, rifampin (rifampicin), St. John's wort (hypericum perforatum)

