1.2 Study objectives and endpoints

The primary objective is to assess the progression-free survival (PFS) as determined by investigator assessment of everolimus plus exemestane and of placebo plus exemestane.

The secondary objectives are:

- To assess PFS in the two treatment arms as determined by a Blinded Independent Review Committee (BIRC)

- To assess overall survival (OS) in the two treatment arms
- To assess the following efficacy endpoints in the two treatment arms based on both local investigator's assessment and BIRC
 - Overall response rate (ORR)
 - Clinical benefit rate (CBR)
 - Time to response and duration of response
- To assess time to deterioration of ECOG Performance Status (PS)
- To characterize the safety and tolerability of everolimus and exemestane versus placebo and exemestane
- Characterize the pharmacokinetics of everolimus pre-dose concentration (C_{min}) and concentration at 2 hours post dose (C_{2h}) when administered in combination with exemestane
- Compare the two treatment arms with respect to pre-dose concentration (C_{min}) and concentration at 2 hours post dose (C_{2h}) of exemestane and to compare the two treatment arms with respect to estradiol (E2) changes from baseline.

For secondary objectives with regards to BIRC assessment and PK analyses, the analysis will not be repeated for the final CSR as per protocol. The results were addressed in the primary CSR (DCO:19-May-2020).

2 Statistical methods

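### The everolimus exposure analysis is worded as one with/without split over CYP3A4/PgP inhibitors and inducers together, so as written it estimates the effect of neither class

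*Protocol*

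**What the plan says.** Protocol section 10.5.3 (Pharmacokinetics) contains three analyses that touch CYP3A4/PgP co-medication.

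- **Everolimus exposure.** Of Cmin and C2h the section says that they "will be analyzed based on with or without concomitant use of CYP3A4/PgP moderate/strong inhibitor or inducer to assess their effect on exposure of everolimus". No further grouping, summary statistic or model is given. In the same section the exemestane comparison is specified fully: log-transformation, ANOVA, ratio and 90% CI.
- **Estradiol.** A model relates everolimus Cmin to the change in estradiol at Week 4, and "This analysis will be repeated adjusted by the concomitant use of moderate/strong CYP3A4/PgP inducer/inhibitor via an appropriate covariate in the model". The levels of that covariate are not stated.
- **Population PK.** The section also says: "Population PK models will be used to identify and quantify potential covariates that influence everolimus PK. Details of this analysis will be covered in a". The sentence ends by pointing to another document, which is not among those supplied.

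On the pharmacology, protocol section 6.4.3 says that everolimus absorption and elimination "may be influenced by products that are substrates, inhibitors, or inducers of CYP3A4 and/or PgP". Section 6.3.2.3 says that systemic imidazole antifungals should be avoided "due to their strong inhibition of everolimus metabolism, therefore leading to higher everolimus exposures". Tables 6-8 and 6-9 list inducers and inhibitors under separate headings.

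The supplied SAP covers the final CSR. Its section 1.2 states: "For secondary objectives with regards to BIRC assessment and PK analyses, the analysis will not be repeated for the final CSR as per protocol". It adds that those results were given in the primary CSR. SAP section 2.4.7 has listed co-medications reviewed and classified as protocol deviations, but sets no grouping for an exposure analysis.

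**The concern.** The stated purpose of the exposure analysis is to learn how these drugs change everolimus levels. Inhibiting the enzyme that clears everolimus raises exposure and inducing it should lower exposure. If patients on either kind of drug form one group, their average reflects the proportion of each, not the effect of either. A result near no difference could then be taken as evidence of no interaction. A result away from it could not be attributed to a class without knowing the mix.

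What is at stake is the interpretation of a co-medication summary in a bridging study for China registration. The efficacy conclusion is not at stake.

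**Working it through.** **No figure to reproduce.** The documents give no sample size, effect size, variability or user count for this analysis. The check is a reading of the text plus an illustration on stated assumptions.

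**Step 1: direction of the two classes.** Protocol section 1.2.1.2.1 describes CYP3A4 as nearly the only enzyme that metabolises everolimus, and section 6.3.2.3 gives the inhibitor direction as upward. The documents state no direction for inducers. Downward is inferred from what induction of a clearing enzyme means.

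**Step 2: is there a rule that separates the classes?** None was found in protocol section 10.5.3 or in the supplied SAP. Some agents also appear on both sides of the protocol's own lists:

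- Ritonavir and lopinavir: moderate inducers and strong inhibitors in Table 6-8.
- Rifampin and St. John's wort: strong inducers in Table 6-8, and both PgP inducers and PgP/CYP3A dual inhibitors in Table 6-9.

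No rule assigns these agents, or patients taking drugs from both classes.

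**Step 3: what a pooled comparison returns.** Assume a geometric mean ratio (users to non-users) as the summary; the plan does not name one. Let p be the share of users on inhibitors, R_inh the inhibitor ratio and R_ind the inducer ratio:

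pooled ratio = exp[p·ln(R_inh) + (1 − p)·ln(R_ind)]

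For R_inh = 2.0 and R_ind = 0.5 this reduces to 2^(2p − 1). At p = 0.75 it is 2^0.5 = 1.41. Across a range of assumed effects:

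| R_inh, R_ind | p = 0.25 | p = 0.50 | p = 0.75 | p = 0.90 |
|---|---|---|---|---|
| 1.5, 0.67 | 0.82 | 1.00 | 1.22 | 1.38 |
| 2.0, 0.5 | 0.71 | 1.00 | 1.41 | 1.74 |
| 2.0, 0.7 | 0.91 | 1.18 | 1.54 | 1.80 |
| 3.0, 0.4 | 0.66 | 1.10 | 1.81 | 2.45 |

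The pooled ratio is exactly 1 at p = −ln(R_ind) / [ln(R_inh) − ln(R_ind)]. For the four rows this is 0.50, 0.50, 0.34 and 0.45.

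**Step 4: effect on what the comparison can show.** Assume 80 everolimus patients (half of about 160 randomised), 10 of them users, and a log-scale SD of 0.6.

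- SE = 0.6 × √(1/10 + 1/70) = 0.203.
- The chance that a 90% CI lies above 1 is about Φ(ln(ratio)/SE − 1.645).
- Ratio 2.0: 0.693/0.203 = 3.42, giving Φ(1.77) = 0.96.
- Ratio 1.41: 0.344/0.203 = 1.69, giving Φ(0.05) = 0.52.
- Ratio 1.00: 0.05 in each direction.

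With a log-SD of 0.4 the first two become 1.00 and 0.81. These figures ignore the extra variance that mixing two classes adds to the user group.

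**The case against.** Several points on the other side stand.

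- **Pooling is not explicit.** A reader might infer that the plan has decided to merge the classes. It has not said so. The sentence could be applied class by class, and Tables 6-8 and 6-9 keep the classes apart. Pooling is the literal reading; the firm statement is that the grouping is unspecified.
- **The covariate belongs elsewhere.** A reader might also infer that one inducer/inhibitor flag is used to assess everolimus exposure. That covariate is in the estradiol model, and an appropriate covariate could have several levels. Only the absence of a definition can be criticised.
- **There is a second route.** The population PK covariate models could estimate the classes separately. Their plan was not supplied, so this cannot be confirmed.
- **Use is restricted.** Section 6.4.3 says "Co-administration with strong inhibitors of CYP3A4 or PgP should be avoided". Exclusion criterion 21 bars recent continuous use of strong agents and names ritonavir and rifampicin. Section 6.4 marks herbal medications as prohibited, which covers St. John's wort. The dual-listed examples should therefore be uncommon. Moderate inhibitors are allowed with caution, however, section 6.4.3 sets no comparable limit on inducers, and SAP section 2.4.7 expects that some patients may take listed drugs.
- **The stakes are low.** Table 3-1 does not list this analysis as an objective of its own, and three groups drawn from about 80 patients may be sparse.

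These points limit the consequence. None of them supplies the missing grouping rule for the comparison that section 10.5.3 states.

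**Conclusion.** The point holds in a limited form. As worded, the everolimus Cmin and C2h comparison mixes drugs with opposite expected effects, so its result depends on the co-medication mix and does not answer its stated question for either class. This rests on the literal reading of one sentence and on inducers acting opposite to inhibitors.

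Two stronger conclusions are not supported. The first is that opposite effects will cancel and hide a real interaction. That needs a near-balanced mix, and the documents give neither the mix nor the effect sizes. With assumed ratios of 2.0 and 0.5 and 90% inhibitor users, the pooled value of 1.74 is diluted but still visible. The second is that pooling biases towards no interaction for both classes. At 75% inhibitor users the pooled 1.41 is on the wrong side of 1 for inducers, which is a different error from shrinkage towards 1.

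The analysis is supportive and the primary PFS estimate does not depend on it. This is a cheap improvement, not a threat to the trial's conclusions.

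**What to change.** Replace the with/without split in protocol section 10.5.3, or the corresponding PK analysis plan, with three groups: moderate/strong inhibitor, moderate/strong inducer, and neither. Summarise Cmin and C2h in each group. Where numbers allow, give the ratio of each user group to neither with a 90% CI, as is already planned for exemestane.

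Add one rule, fixed in advance, that assigns each dual-listed agent (such as ritonavir, lopinavir, rifampin and St. John's wort) and each patient taking both classes to one group, or excludes them. In the estradiol model, state the covariate as separate inhibitor and inducer indicators.

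Because the PK results are already in the primary CSR, first confirm which grouping was used. If it was pooled, re-tabulate the results by class or add a sentence saying that the contrast does not estimate either class's effect.

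The co-medications are already recorded, so the work is recoding and one or two tables. The price is precision. With a log-SD of 0.6 and 70 non-users, a 90% CI for 10 users spans a factor of exp(1.645 × 0.203) = 1.40 either side of the ratio. For 5 users in one class, SE = 0.6 × √(1/5 + 1/70) = 0.278 and the factor is exp(1.645 × 0.278) = 1.58. If a group is too small for an interval, list the individual values.
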